## 1. BACKGROUND, OBJECTIVES, & STUDY DESIGN

Ankle syndesmosis disruption due to ankle trauma is associated with significant pain and disability.  Surgical stabilization procedures typically involve an internal fixation of the distal tibiofibular joint to restore the spatial relationship of the bony structures. Rigid fixation has traditionally been the technique of choice for stabilizing the syndesmosis; however, dynamic fixation options like the TightRope® system (Arthrex®, Naples, United States) have more recently demonstrated some advantage over rigid screw fixation techniques as they attempt to mimic the dynamic nature of the syndesmosis.  Tightrope or flexible fixation is still a non-anatomic reduction and stabilization technique and as such is only an approximation of the syndesmotic ligaments.

Anterior inferior tibiofibular ligament (AITFL) augmentation techniques using nonabsorbable suture materials (*Internal*Brace, Arthrex®, Naples, United States) have been used to supplement syndesmotic fixation in order to more accurately reconstruct the syndesmosis and restore native biomechanics.  Clinical research assessing the use of the *Internal*Brace as an additional stabilization method is lacking and the minimum required stability to achieve successful clinical and patient-reported outcomes remains unclear.

The primary objective of this study is to evaluate the quality of syndesmotic reduction as determined by weight bearing 3-D relative volumetric ratio between ankles in patients undergoing syndesmotic stabilization with and without an *Internal*Brace augmented repair of the AITFL to determine if the technique influences the reduction and postoperative stability of the syndesmosis. This will be compared at both 6-weeks and 3-months post-operation. Our

secondary objectives are 1) to determine whether the addition of the *Internal*Brace augmentation to the traditional TightRope fixation procedure improves short- and long-term patient-reported ankle function and generic health ratings and 2) to explore relationships between syndesmotic volume and patient-reported outcomes across groups.

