#### **Design**

We will use a prospective, two-arm, single-blind, randomized study design to conduct our pilot study. After informed consent, twenty patients will be randomized evenly into a traditional TightRope fixation group or a TightRope fixation with an AITFL augmentation group upon enrollment into the study. As this is a pilot study with a small sample size, block randomization will be used to reduce the risk of unequal group sizes between groups. A researcher who will not otherwise be involved in patient interactions will serve as the randomization coordinator for this trial. They will prepare a randomization schedule using the freely accessible tools available at www.randomization.com. The sequence generator uses block randomization procedures based on the number of interventions and patients needed in each block and creates a schedule based on the patient ID number. Due to the potential emergent nature of injuries involved in this study and a short time between enrollment and surgery, the surgeon may need to acquire the group allocation shortly after enrolling patients to be able to prepare for the surgery and so the schedule will be converted to a Google Document that can then be accessed by the surgeon/PI to reveal the intervention allocation. Since pre-operative and post-operative instructions are the same regardless of the procedure, the participants will be blinded to their intervention group until the completion of the study period.

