#### Withdrawal of Subjects

Participants will be withdrawn from the study if any of the following conditions exist:

- 1. Participant voluntarily withdraws from the study
- 2. Participant death

- 3. Participant who, in the opinion of the PI, would be compromised by continued study participation
- 4. Participant experiences an AE that, in the opinion of the PI, necessitates removal from the study, including unresolved SAE or death
- 5. Participant experiences an intercurrent illness, injury, or other reason that would, in the opinion of the PI, affect the assessment of clinical outcomes or the conduct of the study to a significant degree
- 6. Participant fails to comply with protocol requirements
- 7. Administrative reasons (e.g., PI decides to discontinue the study)

Under these conditions, all patient data will be immediately destroyed. During the consent process, participants will be informed of their right to withdraw from the study at any time for any reason and without prejudice to alternative treatment. For subjects lost to follow-up, the research team should attempt to contact the patient via phone a minimum of three times before considering them lost to follow-up. Participants who withdraw voluntarily or are discontinued by the PI will remain eligible for standard of care treatment by the PI and research team.

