#### 2. STUDY PROCEDURES

Prospective patients will enter the clinic or hospital associated with the study doctor seeking care after ankle trauma. Patient will be moved through clinic/hospital workflow as normal. Once the patient elects to undergo syndesmotic stabilization surgery and is over 18 years of age, study protocol will be triggered as follows:

1. The study doctor will do an initial clinical screening for open fractures or fractures that would require a posterolateral approach during his examination, and if present, the patient will be excluded. If patients are not excluded at this point, the study doctor or another

member of the research team will enter the room and work through the informed consent process with the goal of obtaining the consent. Patient will have ample opportunity to read through documents to their desire. Patient will be asked if they are literate and speak English comfortably and excluded if they do not answer yes to both questions.

- 2. Once the consent is signed, a research team member will review patient's medical history for presence of other exclusion factors: previous ankle surgery, or any contralateral foot or ankle injury. If any exclusion factor is present, consent documents will be shredded.
- 3. If no exclusion factors are present at this point, the following will occur:
  - a. The patient will be issued a participant ID number and will complete the preoperative patient-reported outcomes (PROs) related to their perceived ankle function (The Foot and Ankle Outcome Score) and generic health status (SF-36). These will be administered by a research team member by using either paper format, or a tablet computer through a survey administration software called Surgical Outcome System (SOS).
  - b. The participant ID will be used by the study doctor to verify their randomized group allocation schedule generated by block randomization procedures described above and will be scheduled for their respective surgery.
- 4. Patient will follow typical pre-operative procedures. During the procedure, the patients will be in a supine position so that the fibula and the lateral ankle ligaments can be exposed. The integrity of the AITFL will be examined by the study doctor, and if disrupted the participant will be included in the study and will undergo either the traditional TightRope fixation procedure or the double stabilization procedure (TightRope fixation plus *Internal*Brace augmentation) as assigned and performed by the

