#### STATISTICAL ANALYSIS PLAN

Significance will be set a priori at P = 0.05. All statistical analyses will be conducted using IBM SPSS Statistics, Version 28 (IBM Corporation, Armonk, NY). Descriptive analysis will be performed to describe participant characteristics and independent t-tests will be used to determine differences in pre-operative characteristics and outcomes between groups. In order to compare the 3D syndesmotic volume between groups, the volume ratio will first be calculated for each patient by dividing the syndesmotic volume of the contralateral uninjured ankle by the syndesmotic volume of the operative ankle. Separate t-tests will then be performed to determine whether there are differences between the volumetric ratios, FAOS scores, and SF-36 scores between groups at each collection time point. Pearson-product moment correlations will be conducted to explore relationships between the volumetric ratios and each PRO (FAOS and SF-36) at both 6-weeks and 3-months. Pearson correlation coefficients (r) will be interpreted as (negligible < 0.3, low = 0.3-0.49, moderate = 0.5-0.69, high = 0.7-0.89, very high = 0.9-1.0).

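### The primary volume ratio is tested at 6 weeks and again at 3 months, each at 0.05, with neither visit ranked, no adjustment, and no rule for a split result

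*Combined protocol and SAP*

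**What the plan says.** Section 1 makes the weight-bearing 3-D volume ratio the primary objective and adds: "This will be compared at both 6-weeks and 3-months post-operation". Section 2, step 9, schedules the bilateral weight-bearing CT at those two visits only, so there are exactly two tests of the primary ratio.

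The Statistical Analysis Plan gives one threshold, "Significance will be set a priori at P = 0.05", and one method, "Separate t-tests will then be performed to determine whether there are differences between the volumetric ratios, FAOS scores, and SF-36 scores between groups", applied at every collection time point. It does not order the visits, divide the level, use a joint model, or say what is concluded if one visit is significant and the other is not.

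The Design section describes 20 patients randomised evenly and gives the context: "As this is a pilot study with a small sample size". No power, effect size, SD or between-visit correlation is stated.

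For the patient-reported outcomes (PROs), Section 2, step 3a, says that the patient "will complete the preoperative patient-reported outcomes (PROs) related to their perceived ankle function", together with the SF-36. The follow-up comparisons are nevertheless unadjusted t-tests.

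**The concern.** A single primary question has two unranked answers. If both visits agree, nothing is lost. If they disagree, the plan does not say which is the primary result, and the choice could be made after the data are seen. If a significant difference at either visit is taken as the answer, the 5% level no longer describes the chance of a false primary claim.

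The choice of visit also depends on an unresolved point in the protocol. Section 2, step 8, has patients non-weightbearing for two weeks and then for a further 4 to 6 weeks, that is, to weeks 6 to 8. Step 9 schedules a weight-bearing scan at 6 weeks. Until the two are reconciled, it is unclear how complete or comparable the 6-week scans will be.

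A lesser matter is that the pre-operative FAOS and SF-36 scores are collected but not used in the follow-up analysis, where they could improve precision and account for chance baseline differences.

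**Working it through.** **Inputs.** From the documents: 0.05 per test, two visits, 20 patients, 10 per arm. Assumed, because the documents are silent: two-sided pooled t-tests, between-visit correlation from 0 to 0.9, the same true difference at both visits, and the sizes of that difference. The sample size of 20 cannot be reproduced, because no design inputs are given.

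**1. False positive at either visit, no true effect.** For independent visits: 1 − (1 − 0.05)² = 1 − 0.9025 = 9.75%. By simulation (10 per arm, 18 degrees of freedom), at correlations 0, 0.5, 0.7 and 0.9: 9.7%, 9.1%, 8.5% and 7.2%. With an assumed 8 per arm: 9.8%, 9.2%, 8.4% and 7.2%.

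**2. Chance that exactly one visit is significant.** For independent visits this is 2p(1 − p), where p is the power at one visit; it peaks at p = 0.5. At 1.0 SD the noncentrality is 1.0 × √(10/2) = 2.236, so p = 0.562 and 2 × 0.562 × 0.438 = 49%, almost at the peak. At 0.5 SD, p = 0.184 and 2 × 0.184 × 0.816 = 30%. Simulation supplies the correlated cases:

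| True difference, both visits (assumed) | Split, correlation 0.9 to 0 |
|---|---|
| none | 4% to 10% |
| 0.3 SD | 7% to 18% |
| 0.5 SD | 10% to 30% |
| 1.0 SD | 15% to 49% |
| 1.5 SD | 7% to 20% |
| 2.0 SD | 1% to 2% |

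The upper ends need zero correlation between two scans of the same ankles, which is an extreme assumption.

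**3. Holm across the two visits.** With no effect, the chance of any false positive falls to 4.9%, 4.7%, 4.4% and 3.7% at correlations 0, 0.5, 0.7 and 0.9. Holm does not remove splits: at 1.0 SD it still rejects at exactly one visit in 6% to 38% of trials. The difference detectable with 80% power (noncentral t, 10 per arm) is 1.32 SD at 0.05 and 1.48 SD at 0.025. The second figure is an upper bound for Holm, whose second step uses 0.05.

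**4. Baseline adjustment of a PRO.** The variance of ANCOVA relative to the t-test is (1 − ρ²)(1 + 1/(N − 4)), where ρ is the baseline-to-follow-up correlation (not given in the documents).

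| ρ (assumed) | N = 20 | N = 16 (assumed) |
|---|---|---|
| 0 | 1.06 | 1.08 |
| 0.3 | 0.97 | 0.99 |
| 0.5 | 0.80 | 0.81 |
| 0.7 | 0.54 | 0.55 |

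Break-even is ρ = √(1 − 1/(1 + 1/(N − 4))): √(1 − 1/1.0625) = 0.24 with 20 analysed and √(1 − 1/1.0833) = 0.28 with 16.

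**The case against.** The strongest reply is that this is a 20-patient pilot that makes no power or confirmatory claim. Both visits are pre-specified, so neither can be dropped unnoticed. The objective speaks of comparing at both, and reporting both, with a split read as a time course, is compatible with that wording. Much of this stands, and it limits the severity. It does not close the gap. Pilot status is invoked to justify block randomisation, no section labels the primary comparison exploratory, and a significance threshold is set.

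It is also fair that a split is not always likely. The 15% to 49% range is near the worst case, and at 2.0 SD splits almost vanish.

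Three stronger readings are tempting. A reader might infer that the trial's primary error rate simply is 7% to 10%. The documents do not say that significance at either visit counts as success, so that figure is conditional on such a reading. A reader might infer that the unadjusted PRO t-tests are wrong. They are a valid choice for comparing randomised groups; adjustment is an improvement, and with a low baseline correlation it gains nothing. Finally, a reader might extend the multiplicity point to the PROs. Section 1 places them under its "secondary objectives are 1) to determine whether the addition of the" wording, so they do not compete for the primary conclusion.

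**Conclusion.** The concern holds in a limited form. The primary ratio has two unranked tests at one 0.05 level and no rule for disagreement. Should either visit be allowed to carry the primary claim, the false-positive chance is about 7% to 10%. The frequency of a split ranges from 1% to 49%, according to the true difference and the between-visit correlation, neither of which the documents give. All figures assume two-sided tests and, unless stated, 10 analysed per arm. The severity is minor to moderate: it leaves the reading of the primary result open but does not invalidate the comparisons themselves. The unused PRO baselines are a missed improvement, not an error.

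**What to change.** **Primary ratio.** First reconcile Section 2, step 8 (non-weightbearing to weeks 6 to 8), with step 9 (weight-bearing scan at 6 weeks). Then, before any outcome analysis, name one visit as the single primary comparison at 0.05, with a stated reason, and make the other secondary. This is a change of SAP wording only. The named comparison keeps its power (56% at an assumed 1.0 SD). What is given up is the 64% to 81% chance of a positive at either visit (correlation 0.9 to 0), which exists only at the inflated error rate.

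Alternatively, if both visits stay co-primary, apply Holm and state the conclusion separately for each. This controls the error rate but ranks neither visit, so the per-visit wording is needed. The cost is a rise in the detectable difference from 1.32 SD to at most 1.48 SD, and the chance of any positive at 1.0 SD becomes 51% to 68%.

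**PROs, as an improvement.** Replace the follow-up t-tests for FAOS and SF-36 with ANCOVA on arm and that score's pre-operative value, and report the arm difference with a 95% confidence interval. This needs no new data and runs in the named SPSS software. It costs one degree of freedom and at most about 6% in variance with 20 analysed (8% with an assumed 16). Precision improves once the baseline correlation exceeds about 0.24 to 0.28.

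### The volume–PRO correlations have no term for arm; if the arms are pooled, a treatment effect on both variables can appear as a volume–outcome relationship (minor)

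*Combined protocol and SAP*

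**What the plan says.** Section 1 (Background, Objectives, & Study Design) gives as the second of two secondary objectives "to explore relationships between syndesmotic volume and patient-reported outcomes across groups". The Statistical Analysis Plan meets it with one sentence: "Pearson-product moment correlations will be conducted to explore relationships between the volumetric ratios and each PRO", where the PROs and visits are "each PRO (FAOS and SF-36) at both 6-weeks and 3-months". It names no covariate, partial correlation or by-arm analysis, and does not say whether r is computed over all patients or within each arm.

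The same section compares the same variables by arm: "Separate t-tests will then be performed to determine whether there are differences between the volumetric ratios, FAOS scores, and SF-36 scores between groups". It sets the level ("Significance will be set a priori at P = 0.05") and labels the size of r in bands that begin "negligible < 0.3, low = 0.3-0.49, moderate = 0.5-0.69".

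Under Design, "twenty patients will be randomized evenly into a traditional TightRope fixation group" or the augmented group, and the trial is described as a pilot.

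**The concern.** The objective asks whether patients whose operated syndesmosis is closer in volume to the uninjured side also report better function and health. A Pearson r over both arms mixes two sources of covariance: the relation among patients given the same operation, and the difference between the arms on both variables.

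Both visits come after the randomised surgery. The effect of arm on the ratio is the primary question, and its effect on PROs is the first secondary question. Arm is therefore a possible common cause of the two variables, and the plan itself examines both effects. If augmentation shifted both, a pooled r could be read as evidence that volume tracks outcome when it shows only that one arm did better on each. If the arm effects ran against the within-arm relation, a real relation could be hidden.

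At stake is the reading of one secondary objective, which carries a significance level and strength labels. The comparisons between arms are not affected.

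**Working it through.** **Inputs from the documents.** 20 patients, 10 per arm (Design); level 0.05, taken as two-sided because sidedness is not stated (SAP); the SAP's bands for r.

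**Assumed inputs.** The documents give no effect size, SD or expected r, so there is no figure of the plan's own to reproduce. Let d1 and d2 be the arm effects on ratio and PRO in within-arm SD units, shown over a range, and let ρ be the within-arm correlation. Data are taken as normal.

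**Formula.** With 1:1 allocation the arm difference adds d1·d2/4 to the covariance and d²/4 to each variance:

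pooled r = (ρ + d1·d2/4) / √[(1 + d1²/4)(1 + d2²/4)]

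**No within-arm relation (ρ = 0), equal effects d on both variables.** The formula reduces to (d²/4)/(1 + d²/4). False-positive rates come from 100,000 simulated trials of 10 per arm. The critical |r| at n = 20 is 0.444 pooled and 0.456 adjusted for arm.

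| d on both | Pooled r | False positives, pooled | False positives, arm-adjusted |
|---|---|---|---|
| 0.5 | 0.0625/1.0625 = 0.06 | 6% | 5% |
| 0.8 | 0.16/1.16 = 0.14 | 9% | 5% |
| 1.0 | 0.25/1.25 = 0.20 | 14% | 5% |
| 1.32 | 0.4356/1.4356 = 0.30 | 27% | 5% |
| 2.0 | 1/2 = 0.50 | 70% | 5% |

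The expected r leaves the SAP's *negligible* band at d = 2√(0.3/0.7) = 1.31 on both variables. For scale, 1.32 SD is the difference that a t-test with 10 per arm detects with 80% power; it is not an expected effect.

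**Effect on one variable only** (d1 = 1.5, d2 = 0, ρ = 0): the numerator is 0, so pooled r = 0, and the false-positive rate is 5%.

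**Masking** (ρ = 0.5, opposite effects):
- 0.8 SD: (0.5 − 0.16)/1.16 = 0.29.
- 1.32 SD: (0.5 − 0.4356)/1.4356 = 0.045.

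**Arm acting on PROs wholly through volume** (ρ = 0.5, d1 = 1.32, d2 = 0.5 × 1.32 = 0.66): the numerator is 0.5 + 0.2178 = 0.7178, the denominator is √(1.4356 × 1.1089) = 1.262, and pooled r = 0.57. The arm-adjusted value is 0.50. Here the between-arm part is not an artefact.

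**Precision.** For r = 0.30 at n = 20, the Fisher interval is tanh(0.3095 ± 1.96/√17), which is −0.16 to 0.66.

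**The case against.** The best case for leaving the plan alone has four parts.

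- **Pooling is not stated.** This stands: a reader might infer that the SAP prescribes one r over all 20 patients, and it does not. The wording of the objective makes pooling the natural reading, since the SAP uses a different phrase when it means an arm comparison. If within-arm correlations were intended, the sentence still needs to say so.
- **The distortion is conditional and often small.** This stands for the expected r. It needs arm effects on both variables, and below about 1.3 SD on each it stays in the *negligible* band. But a single observed r will be labelled. At 0.8 SD on both with no within-arm relation, the pooled r is 0.3 or more in about 25% of trials, against about 10.5% for the adjusted r.
- **The between-arm part may be genuine.** This is the strongest part, and it stands. If augmentation helps patients by way of volume, the arm contrast is real evidence on volume and outcome. A reader might infer that the pooled r is simply wrong and should be replaced. The documents do not support that: replacement would change the quantity being estimated. What remains is that the pooled r alone cannot tell this case from an effect by another route.
- **The analysis is exploratory.** The Design section says "As this is a pilot study with a small sample size", and at n = 20 imprecision outweighs the bias at moderate arm effects. This limits the severity. It does not remove the need for a defined analysis of a stated objective.

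**Conclusion.** The point holds in a limited form. The SAP plans plain correlations between two post-randomisation variables, leaves the pooling unstated and has no term for arm. A treatment effect on both can therefore enter the pooled r. Under the assumptions above, the induced r runs from 0.06 to 0.50 for equal effects of 0.5 to 2 SD, and is 0 if only one variable is affected. The false-positive rates apply only where arm changes PROs by routes other than volume.

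Two stronger readings should be avoided. One is that the trial is designed so that the arms will differ: the objectives put both effects as open questions. The other is that the correlation will be used to establish volume as a marker of outcome: nothing in the documents proposes that.

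Severity is minor. No primary conclusion depends on these correlations.

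**What to change.** Amend the correlation sentence in the Statistical Analysis Plan to say that, at 6 weeks and at 3 months:

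1. The pooled Pearson r is computed over both arms and labelled as pooled.
2. It is accompanied by the partial correlation controlling for arm, or equivalently by the regression of each PRO on ratio plus arm.
3. Both estimates carry 95% confidence intervals, with scatterplots marked by arm.
4. A volume–PRO relation is claimed as independent of treatment only if the arm-adjusted estimate supports it.

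The cost is one degree of freedom (18 to 17) and a slight loss of precision. With no arm effects and a true r of 0.5, power falls from 64% by about 2 to 3 percentage points. No new data are needed. The adjusted r leaves out any genuine effect of arm acting through volume, which is why the pooled r is kept beside it.

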- study doctor. If AITFL disruption is not confirmed at this point, the patient will be excluded from the study; however, will still undergo the appropriate stabilization procedures necessary for treating their traumatic injury. If patients are excluded at this point, they will be informed post-operatively, and all study documents will be shredded.
- 5. If participants are not excluded and are assigned to the traditional TightRope fixation group: the fibular fracture will be stabilized with fixation and the plate will be applied laterally to the fibula. The syndesmosis is directly reduced and held in a stable position with the TightRope device. The syndesmosis is then restressed and examined to ensure that it is stable and reduced.
- 6. If participant is not excluded and is assigned to the TightRope fixation plus *Internal*Brace augmentation group: the FiberTape portion of the *Internal*Brace will be threaded through the distal fibular plate which will then be applied. The fibular fracture will be stabilized with fixation and the plate applied laterally to the fibula. The syndesmosis will be directly reduced and held in a stable position with the TightRope device. A 3.4 mm drill and 4.75 mm tap are used to make a small hole in the distal tibia at the anatomic origin of the anterior inferior tibiofibular ligament. A 4.75 mm SwiveLock anchor is then used to set the tension of the AITFL repair over the top of the torn AITFL ligament. The syndesmosis is then restressed and examined to ensure that it is stable and reduced.
- 7. Pre-operative PRO data for all eligible participants will be entered into a spreadsheet by a research team member along with basic demographic information (age, biological sex, height, weight, race), involved side (right or left ankle), type of procedure (traditional or traditional plus augmentation), and any relevant surgical notes.

- 8. All participants will be given the same post-operative directives regarding treatments and care which includes being non-weightbearing and immobilized for the first two weeks after surgery. At this point, the patients will begin a physical therapy program incorporating passive modalities and gentle range-of-motion exercises. Patients will remain non-weightbearing in a post-operative cam boot for the next 4-6 weeks.

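### Secondary objective 2 relies on Pearson r with the signed volume ratio alone; adding a correlation with distance from side-to-side symmetry would guard against a two-sided relationship being labelled negligible

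*Combined protocol and SAP*

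**What the plan says.** Section 1 (Background, Objectives, & Study Design) sets the primary objective as to "evaluate the quality of syndesmotic reduction as determined by weight bearing 3-D relative volumetric ratio between ankles". The second of its secondary objectives is "to explore relationships between syndesmotic volume and patient-reported outcomes across groups".

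The Statistical Analysis Plan forms the ratio by "dividing the syndesmotic volume of the contralateral uninjured ankle by the syndesmotic volume of the operative ankle". A value of 1 is therefore a match, a value below 1 means the operative side is larger, and a value above 1 means it is smaller. For objective 2, "Pearson-product moment correlations will be conducted to explore relationships between the volumetric ratios and each PRO (FAOS and SF-36", at both imaging visits. Coefficients are graded as "negligible < 0.3, low = 0.3-0.49, moderate = 0.5-0.69, high = 0.7-0.89, very high = 0.9-1.0". The same section also says "Significance will be set a priori at P = 0.05".

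The plan defines no distance-from-1 measure, scatterplot, linearity check, or rank or curved alternative for this objective.

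**The concern.** If the uninjured ankle is the reference, quality of reduction is most naturally read as closeness to 1. Pearson r on the signed ratio measures something else: whether the PRO rises or falls steadily from a wider to a narrower operative side. If function were best near 1 and fell away on both sides, the two limbs would cancel and r would tend to zero however strong the link. The plan's scale would then call that negligible.

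Section 1 says it is unclear how much stability is needed for good patient-reported outcomes. A misleading negligible label would bear on that question, and it would be likeliest when reductions centre well on the uninjured side.

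**Working it through.** The plan gives no expected r, ratio mean, ratio SD or power for this analysis, so there is no stated figure to reproduce.

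**Inputs from the documents**
- n = 20 (Design: "twenty patients will be randomized evenly into a traditional TightRope fixation group or a TightRope fixation with an AITFL augmentation group"). Both arms are pooled here, reading objective 2 as across groups.
- R = uninjured volume / operative volume.
- Negligible means below 0.3. The cut-offs carry no absolute-value sign; |r| is used here.
- Significance level 0.05, taken as two-sided because the plan does not say. With 18 df, critical |r| = 2.101 / √(18 + 2.101²) = 0.444.

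**Assumptions, not in the documents**
- L = ln R is normal with SD s and mean c·s, so c is the distance of the centre from symmetry in SDs.
- PRO = -|L| + noise, with noise SD = SD(|L|) × √(1/ρ² - 1), so that the true correlation of PRO with |L| is -ρ. For ρ = 0.7 the multiplier is √(1/0.49 - 1) = 1.02.
- 40,000 simulated trials per setting.

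**Step 1: exact example.** Take 20 ratios evenly spaced from 0.70 to 1.30, with the PRO an exact linear function of |R - 1|. Pearson r is 0.00 with R, -1.00 with |R - 1| and -0.97 with |ln R|. Each point below 1 cancels its mirror image above 1.

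**Step 2: simulation under two-sided harm, ρ = 0.7, s = 0.15**

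| Centre of ratios | Signed r: negligible | Signed r: significant |
|---|---|---|
| on 1 | 64% | 16% |
| 0.5 SD above 1 | 26% | 55% |
| 0.5 SD below 1 | 37% | about 42% |
| 1 SD above 1 | 5% | 86% |
| 1 SD below 1 | 9% | 78% |
| 2 SD above 1 | no loss | no loss |

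With |L| as the x-variable, about 1% are negligible and about 95% significant throughout. Centred on 1, with s from 0.05 to 0.30, signed r is negligible in 61% to 64% and significant in 16% to 18%. Mean signed r is about -0.44 with the centre 0.5 SD above 1 and about +0.36 with it 0.5 SD below, so even its sign depends on where the ratios centre.

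**Step 3: weaker links, centred on 1.** At ρ = 0.5, negligible in about 70% (signed) against 15% (distance). At ρ = 0.3, 76% against 48%.

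**Step 4: the opposite truth, correlation 0.7, centred on 1.** If the PRO is linear in signed L, the distance measure is negligible in about 65% of trials and signed r in 1%. If only widening harms, 40% against 8%.

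**Step 5: precision.** At n = 20 an observed r of 0.3 has a 95% interval of tanh(0.310 ± 1.96/√17), about -0.16 to 0.66.

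**The case against.** The cancellation needs two things that the documents do not say: that operative volumes fall on both sides of 1, and that a smaller volume harms function as a larger one does. A reader might infer compression from the augmentation step in Study Procedures, where an anchor "is then used to set the tension of the AITFL repair over the top of the torn AITFL ligament". That describes tensioning; it does not mention over-tightening or harm from it. The only reduction failure named among the risks is re-diastasis, which is widening. Section 1 asks about the minimum stability required, a question that runs in one direction and that a signed ratio suits. This stands: two-sided harm is an assumption.

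The simulation is also kind to the concern. It uses a symmetric V shape and a correlation that is high on the plan's own scale. Noise is rescaled at each SD to hold that correlation, so the SD range barely tests anything. At a true correlation of -0.3 the distance measure is itself negligible in 48%, so small n is part of the problem. This stands too.

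A reader might go further and want |log ratio| to replace the signed ratio. Step 4 rules that out: when the link is one-directional, the distance measure alone fails about as badly as signed r does under two-sided harm.

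Finally, the objective is exploratory, in a 20-patient pilot, and nothing prevents a later scatterplot. That lowers the priority. It does not remove the value of choosing the measure before the data are seen.

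**Conclusion.** The point holds as a conditional one. The plan treats the ratio as reduction quality relative to the uninjured ankle but explores its link with PROs only through a straight line in the signed ratio. If harm is two-sided and the true correlation with |log ratio| is -0.7, the chance of a negligible label at n = 20 runs from 61% to 64% with ratios centred on 1 down to no loss at 2 SD above 1. The documents give no ratio mean or SD, so they do not show where in that range this trial would fall.

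It would be too strong to say that the plan is in error, that it will miss a real relationship, or that volume and function are related in both directions; the documents support none of these. The primary comparison does not use this correlation and is not affected. This is a cheap improvement of low priority.

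**What to change.** In the Statistical Analysis Plan, for secondary objective 2:
- Keep the Pearson r of each PRO with the signed ratio as planned.
- Add a pre-specified Pearson r of each PRO with |log volume ratio|, and a scatterplot, at 6 weeks and 3 months.
- Label both coefficients as exploratory.
- Describe a relationship as negligible only if both are below 0.3 in absolute value.

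The data are already being collected, so the direct cost is a sentence or two and one extra coefficient per PRO and visit. The statistical cost is multiplicity. As an example, five FAOS subscales plus PCS and MCS at two visits give 7 × 2 = 14 coefficients, which become 28. With no true association, the expected number significant at an unadjusted 0.05 rises from 14 × 0.05 = 0.7 to 28 × 0.05 = 1.4. Requiring both coefficients to be weak also makes the negligible label harder to earn when nothing is there. The report should acknowledge both effects.
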